10.1 Analysis set

All analyses are performed for the Plexa ProMRI S DX analysis set⁹⁷

10.2 Variables

10.2.1 Lead handling assessment

CIP chapter 8.1.4.6 Assessment of Plexa S DX lead handling (if applicable)

During implantation, the handling of the Plexa S DX lead will be assessed by the implanting physician.

Implantation / Assessment of Plexa Pro MRI S DX lead handling

Data file, identifier patient_display_id_full	Notes	Variable name	Variable label	Variable level	Nominal values
implantation	descr.	DUFLXAS01 [REDACTED]	Flexibility of the Plexa ProMRI S DX	nominal	 Very good  Good  Adequate  Poor  Very poor
	descr.	DUPSHAS	Push-ability of the Plexa ProMRI S DX		
	descr.	DUPSBHAS	Positioning behavior of the Plexa ProMRI S DX		
	descr.	DUERBHAS	Extension/retraction behavior of the Plexa ProMRI S DX screw		
	descr.	DUXRVSAS01	X-ray visibility of the extended screw of the Plexa ProMRI S DX		
	descr.	DUFXBHAS	Fixation behavior of the Plexa ProMRI S DX		
	descr.	DUXRVSAS02	X-ray visibility of the Plexa ProMRI S DX in its final position		
	descr.	DUSTLHAS	Stylet handling in regard to the Plexa ProMRI S DX?		

Data file, identifier patient_display_id_full	Notes	Variable name	Variable label	Variable level	Nominal values
implantation	case listings	COFLXAS01 [REDACTED]	Please specify flexibility of the Plexa ProMRI S DX	text	n.a.
	case listings	COPSHAS	Please specify the push-ability of the Plexa ProMRI S DX		
	case listings	COPSBHAS	Please specify the positioning behavior of the Plexa ProMRI S DX		
	case listings	COERBHAS	Please specify extension/retraction behavior of the Plexa ProMRI S DX screw		
	case listings	COXRVSAS01	Please specify X-ray visibility of the extended screw of the Plexa ProMRI S DX		
	case listings	COFXBHAS	Please specify fixation behavior of the Plexa ProMRI S DX		
	case listings	COXRVSAS02	Please specify X-ray visibility of the Plexa ProMRI S DX in its final position		
	case listings	COSTLHAS	Please specify stylet handling in regard to the Plexa ProMRI S DX		

10.2.2 Atrial sensing assessments

Lead Measurements / System performance RA

The following analyses have to be performed for implantation, pre-hospital_ discharge, 3m follow-up, 6m follow-up, and 12m follow-up, whereby the variables labels have to be indicated, respectively.

Data file, identifier PRVISIT & patient_display_id_full	Notes	Variable name	Variable label	Variable level	Nominal values
lead_measurement	no report	PRVISIT	Visit	nominal	 Implantation  Pre-Hospital Discharge  3m Follow-up  6m Follow-up  12m Follow-up
	descriptive	DURASAAD	Adequate RA sensing	nominal	 Yes  No
	descriptive	DURASARE	Reason for inadequate RA sensing	nominal	 No intrinsic signal  Oversensing  Undersensing  Other

10.2.3 Adverse events related to the Plexa S DX per event

Data file identifier record_id & patient_ display_id_full	Notes	Variable name	Variable label	Variable level	Nominal values
data_SAR	case listings for the data below	imp_PRIMSTDT	Date of procedure (Implantation CRF)	date	n.a.
device_log_ details	No report	DIRVMDL	RV lead model	nominal	...
		record_id	Record ID	nominal	...
adverse_ event	No report	AEDVID	Please enter the related Device ID(s) from the Device Log below. Use "," to separate multiple entries.	nominal	...
NOTE that AEDVID may contain multiple device IDs	case listings for AEDVID = record_id with DIRVMDL contains "Plexa" and DIRVMDL contains "DX"	AERELIDV	AE is related to the investigational device	nominal	 Not related  Unlikely  Possible  Probable  Causal relationship
		AERELIPR	AE is related to the investigational device procedure	nominal	 Not related  Unlikely  Possible  Probable  Causal relationship
		AESLIFE	a life-threatening illness or injury	nominal	 Yes  No
		AESDISAB	a permanent impairment of a body structure or body function	nominal	 Yes  No
		AESHOSP	in-patient or prolonged hospitalization	nominal	 Yes  No
		AESMIE	medical or surgical intervention to prevent life-threatening illness or injury or permanent impairment to a body structure/body function	nominal	 Yes  No
		AESCONG	Event led to fetal distress, fetal death or a congenital abnormality or birth defect	nominal	 Yes  No
		AEOUT	Outcome	nominal	 Resolved  Resolved with sequelae  Death  Ongoing  Ongoing at study termination  Unknown
		COAEOUT	Please specify	text	n.a.
		AEENDT	Date of resolution/Date of death	date	n.a.

10.2.4 Early detection of atrial fibrillation (episodes)

Data file identifier record_id & patient_ display_id_full	Notes	Variable name	Variable label	Variable level	Nominal values
tachyarrhythmia_ episode	descriptive	CVAFON	New onset of AF	nominal	 Yes  No
	descriptive and 2x2 table CVAFON x CEFUAFHM	CEFUAFHM	AF episode detected by Home Monitoring prior to follow-up visit		 Yes  No

10.3 Treatment of Missing and Spurious Data

See general definitions in chapter 5.4.

10.4 Exclusion of Particular Information

See general definitions in chapter 5.5.

10.5 Descriptive Analyses

See general definitions in chapter 5.1 and notes previous variable tables.

10.6 Hypotheses & Statistical Tests

There are no pre-defined statistical hypotheses.

11 Primary Endpoint: Cor Family-related SADE-free rate until 3-month follow-up

11.1 Analysis set

All analyses are performed for the Cor family analysis set⁹⁸ excluding the following patients:

CIP chapter 11.12 Exclusion of data from confirmatory data analysis

Exclusion of patients from the analysis set of the primary hypothesis:

- No data is allowed to be collected and included in the absence of a documented informed consent*⁹⁹
- Patients that are erroneously enrolled despite violation of inclusion or exclusion criteria at the time of enrollment*¹⁰⁰
- Patients without primary endpoint but premature study termination as defined for the primary endpoint*¹⁰¹

CIP chapter 7.2.1 Primary endpoint and hypotheses: Cor Family-related SADE-free rate until 3-month follow-up

The following patients are not included in the analysis set for this endpoint:

Patients without endpoint but premature study termination before or exactly at 61 days after implantation (3 months defined as 92 days after implantation – 30 days would still be in accordance to the CIP) are not included in the analysis set to avoid an over-estimation of the SADE-free rate.

11.2 Variables

CIP chapter 7.2.1 Primary endpoint and hypotheses: Cor Family-related SADE-free rate until 3-month follow-up

SADEs will be adjudicated by an internal adjudication board, whereby the seriousness and device relatedness will be re-examined. If any amply documented external physical influence (e.g. accident, sport, twiddling) or medical AE caused the SADE, it does not contribute to this endpoint.

Data file record_id & patient_display_id_full	Notes	Variable name	Variable label	Variable level	Nominal values
event_evaluation	no report	AESTDT	Onset date	date	n.a.
event_evaluation	no report	AERELSET ¹⁰²	Adverse Event is relevant for SADE endpoint	nominal	 Yes  No
event_evaluation	no report	AERELPET ¹⁰³	Adverse Event is relevant for primary endpoint	nominal	 Yes  No

Data file record_id & patient_display_id_full	Notes	Variable name	Variable label	Variable level	Nominal values
data_SAR	no report	date_implantation_SAR	Date of implantation	date	n.a.
data_SAR	no report	date_censoring_SAR	Date of censoring (latest date of AE onset, AE resolution, implantation, PHD, 3m FU, 6m FU, 12m FU, or date of study termination)	date	n.a.
data_SAR	descriptive & inferential	any_primep_SAR ¹⁰⁴	Any primary endpoint within the pre-specified time-period	nominal	 Yes  No

11.3 Treatment of Missing and Spurious Data

See general definitions in chapter 5.4.

11.4 Exclusion of Particular Information

CIP chapter 7.2.1 Primary endpoint and hypotheses: Cor Family-related SADE-free rate until 3-month follow-up

SADEs will be adjudicated by an internal adjudication board, whereby the seriousness and device relatedness will be re-examined. If any amply documented external physical influence (e.g. accident, sport, twiddling) or medical AE caused the SADE, it does not contribute to this endpoint. SADEs that occur later than the 3-month follow-up, and SADEs with onset date later than or exactly at 123 days after implantation (3 months defined as 92 days after implantation + 30 days would still be in accordance to the CIP) in case the 3-month follow-up was not conducted or conducted outside the specified time interval do not contribute to this endpoint.

11.5 Descriptive Analyses

See general definitions in chapter 5.1 and notes previous variable tables.

11.6 Hypotheses & Statistical Tests

CIP chapter 7.2.1 Primary endpoint and hypotheses: Cor Family-related SADE-free rate until 3-month follow-up

The safety of the Cor Family ICDs will be evaluated by asking the investigator to record any adverse event. While all adverse events have to be recorded throughout the study, only the Serious Adverse Device Effects (SADE) possibly or securely related to the Cor Family devices (SADE-d_{Cor}) until 3-month follow-up are counted for this primary endpoint. Purely procedure related Serious Adverse Device Effects (SADE-p_{Cor}) are not counted.

... The primary hypothesis evaluates the SADE-d_{Cor} free rate (Cor_{SADE_free}). It is expected, that the rate will be significantly above 90% ...

CIP chapter 11.1 Statistical design, method and analytical procedures

To test the primary hypothesis an exact binomial tests is carried out. Additionally, an exact 2-sided 95% confidence interval will be generated.

12 Sec. Endpoint 1: Kaplan-Meier estimate for the Cor Family related SADE-free rate

12.1 Analysis set

All analyses are performed for the Cor family analysis set¹⁰⁵ excluding the patients that are erroneously enrolled despite violation of inclusion or exclusion criteria at the time of enrollment as defined for the primary endpoint analysis.

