1. A Kaplan-Meier estimate for the SADE-free rate at 3 and 12 months will be performed as a sensitivity analysis for the primary endpoint.
2. The Automatic LV VectorOpt test will be evaluated with regard to time savings, usability and acceptance criteria. This test was chosen as endpoint because it is a new feature that consists in a further development of the already known manual LV VectorOpt test which was investigated in the BIO|MASTER.Edora Family study.
3. The CRT AutoAdapt feature will be evaluated with regard to its programming, the behavior of the algorithm, usability and acceptance criteria. While CRT AutoAdapt aims at improving hemodynamics, it is not expected that significant effects on hemodynamics can be detected due to the small sample size and relatively short duration of this investigation. However, data on the functionality and acceptance of the feature contribute to this secondary endpoint that was chosen in order to gain more insight in the clinical use of this new feature.

¹ MEDDEV 2.7/1 Rev. 4

² MEDDEV.2.12/2 rev.2: 2012 Guidelines on Post Market Clinical Follow-up

BIOTRONIK SE & Co.KG // BIO|MASTER.Cor Family

Automatic LV VectorOpt and CRT AutoAdapt are new features that were implemented for the first time in BIOTRONIK devices and therefore chosen as secondary endpoints.

Another focus of the study is the data collection for the Plexa S DX lead with DF4 connection. For this reason data of interest are recorded to assess the atrial sensing performance and lead related adverse events but also the handling assessment during the implantation.

The product design of the DF4 variant of Plexa S DX is identical to the Plexa S DX DF-1 lead, except for the connector. In the BIO|MASTER.Ilivia Family/Plexa study, 27 Plexa S DX DF-1 leads were analyzed and already provided enough clinical data for the safety and efficacy of the DX lead variants²⁸. Therefore, 30 Plexa S DX leads with DF4 connection are considered to be sufficient for the evaluation in this study.

The decision to include the Plexa S DX lead into the Master Study for the Cor Family devices is based on the fact that Acticor/Rivacor VR-T DX is the only device on the market that is compatible with this new DX lead with DF4 connection. Thus, the requirements for a PMCF for both devices were combined in one study.

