7.2.2 Secondary endpoints

7.2.2.1 Secondary endpoint 1: Kaplan-Meier estimate for the Cor Family related SADE-free rate

The Kaplan-Meier method will be applied to estimate the 3-month SADE-free rate at 92 days after implantation (sensitivity analysis of the primary endpoint) and the 12-month SADE-free rate at 365 days after implantation. Thereby all patients will be included in the analysis.

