8.1.2 Measures taken to minimize or avoid bias

The clinical investigation is designed and will be conducted, analyzed, and reported based on an internal Standard Operating Procedure (SOP) system to minimize and avoid any bias.

A Kaplan-Meier estimate for the SADE-free rate at 3 months was included as secondary endpoint in order to account for a potential bias that might arise if the scheduling of the 3-month follow-ups within the allowed time window (± 30 days) is unbalanced.

A maximum number of patients per investigational site is defined in order to avoid a center effect (see section 11.13).

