11.9 Specification of subgroups

For this clinical investigation there is no specification of subgroups in the sense that analyses will be repeated for subsets of the pre-specified analysis set. However, there are different analysis sets defined for the primary and secondary endpoints.

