11.12 Exclusion of data from confirmatory data analysis

In the following cases, data are to be excluded from analysis or prevented from inclusion into analysis:

- Exclusion of patients from the analysis set of the primary hypothesis:
 - No data is allowed to be collected and included in the absence of a documented informed consent
 - Patients that are erroneously enrolled despite violation of inclusion or exclusion criteria at the time of enrollment
 - Patients without primary endpoint but premature study termination as defined for the primary endpoint are not included in the analysis set to avoid an over-estimation of the SADE-free rate.
- Exclusion of data from patients included in the analysis set of the primary hypothesis:
 - Any event occurred later than the pre-specified time window after implantation as defined for the primary endpoint.
 - SADEs will be adjudicated by an internal adjudication board, whereby the seriousness and device relatedness will be re-examined. If any amply documented external physical influence (e.g. accident, sport, twiddling) or other causative AE led to the SADE, the SADE does not contribute to the endpoint.

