18.5.1 Definition of endpoint-related SADEs

The SADE-free rate calculated for the primary endpoint will be based on the total number of subjects with at least one SADE related to a Cor Family ICD until 3-month follow-up. SADEs that occur later than the 3-month follow-up, and SADEs with onset date later than or exactly at 123 days after implantation in case the 3-month follow-up was not conducted or conducted outside the specified time interval do not contribute to this endpoint.

However, SADEs until the 12-month follow-up will contribute to secondary endpoint 1.

Endpoint-related SADEs are complications, which are device-related adverse events that are corrected using invasive measures or require invasive measures to correct or which result in the loss of significant device function. Device-related adverse events, which are corrected by non-invasive measures (e.g. reprogramming) are considered observations and will not contribute to the primary endpoints.

Only SADEs directly related to the device (SADE-d) will be included in the endpoint. SADEs which are securely related to the implantation procedure (SADE-p) (e.g. pocket infection, etc.) will not be considered for the primary endpoint. Inappropriate ICD therapies which are not related to a device defect (e.g. if the device function is according to device specification) will also not be considered for primary endpoint analysis. Furthermore 'Twiddler's' syndrome will not be considered for the endpoint analysis. If any amply documented external physical influence (e.g. accident, sport, twiddling) or medical AE caused the SADE, it does not contribute to this endpoint.

All serious adverse device effects that meet these primary endpoint criteria (confirmed by an internal endpoint committee) for the Cor Family ICDs will be included in the primary endpoint event analysis. Adverse events with a device relation of "not related" will not contribute to or be included in the evaluation of the primary safety endpoint.

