12.6 Hypotheses & Statistical Tests

CIP chapter 7.2.2.1 Secondary endpoint 1: Kaplan-Meier estimate for the Cor Family related SADE-free rate

The Kaplan-Meier method will be applied to estimate the 3-month SADE-free rate at 92 days after implantation (sensitivity analysis of the primary endpoint) and the 12-month SADE-free rate at 365 days after implantation. Thereby all patients will be included in the analysis.

The pointwise 95% confidence interval has to be calculated via the loglog transformation.

13 Sec. Endpoint 2: Automatic LV VectorOpt test (CRT only)

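### SAP 12.1 drops eligibility violators from the Kaplan-Meier analysis that protocol 7.2.2.1 says includes all patients, so no planned SADE-free rate covers them

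*SAP*

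**What the plan says.** **Kaplan-Meier set.** Protocol 7.2.2.1 defines secondary endpoint 1 as Kaplan-Meier estimates of the Cor Family-related SADE-free rate at days 92 and 365, and adds: "Thereby all patients will be included in the analysis". SAP 12.6 reproduces that sentence and then specifies the interval: "The pointwise 95% confidence interval has to be calculated via the loglog transformation". SAP 12.1 starts from the Cor family analysis set, which SAP 7.3 bases on an implantation attempt, and continues "excluding the patients that are erroneously enrolled despite violation of inclusion or exclusion criteria at the time of enrollment". SAP 12.4 (Exclusion of Particular Information) refers only to SAP chapter 5.5.

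**Where the exclusion comes from.** Protocol 11.12, copied in SAP 5.5, lists it under the label "Exclusion of patients from the analysis set of the primary hypothesis". SAP 11.1 applies it to the primary set. Protocol 11.9 notes that "there are different analysis sets defined for the primary and secondary endpoints". Protocol 18.5.1 says that "SADEs until the 12-month follow-up will contribute to secondary endpoint 1", without mentioning eligibility.

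**Purpose.** Protocol 5.3 says the Kaplan-Meier estimate "will be performed as a sensitivity analysis for the primary endpoint". Protocol 8.1.2 says the 3-month estimate was added "in order to account for a potential bias that might arise if the scheduling of the 3-month follow-ups" within the allowed window is unbalanced.

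**Enrollment stop.** Protocol 20.1 allows enrollment to end once 114 patients are in the primary analysis set. It then describes members as patients with at least 61 days in the study after implantation, or with an earlier primary endpoint.

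**The concern.** SAP chapter 12 gives two populations for one analysis: everyone in 12.6, and everyone except eligibility violators in 12.1. A programmer will follow the analysis-set section and so will not produce what the protocol promises. The protocol does not authorise the narrower set, because its eligibility exclusion is confined to the primary hypothesis.

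The study is meant to find residual device risks. A patient who received a Cor Family device despite an eligibility violation was exposed to those risks. That patient is absent from the primary rate, from its 3-month Kaplan-Meier counterpart, and from the 12-month Kaplan-Meier rate, which has no substitute in the plan.

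A smaller mismatch of the same kind sits in protocol 20.1. Its description of who counts toward 114 omits the eligibility exclusion that 11.12 applies to that set. It also admits a patient who leaves at exactly day 61 without an endpoint, whom 7.2.1 excludes.

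**Working it through.** **1. The planned figure this touches.** Inputs: SADE-free rate 90% under the null and 98% assumed (protocol 7.2.1, 11.2); exact binomial test at two-sided 5% with power of at least 95% (11.1, 11.3); about 10% not evaluable (11.4). Let X be the number of patients with an event.

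- n = 114: the test passes with at most 5 events. P(X ≤ 5 | 114, 0.10) = 0.0239, below 0.025. Power = P(X ≤ 5 | 114, 0.02) = 97.3%.
- n = 113: at most 4 events pass, and power is 92.3%.
- n = 114 to 127: the lowest power is 95.8%, at n = 126.
- 114 / 0.90 = 126.7, rounded up to 127.

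Both 114 and 127 reproduce.

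**2. The population texts side by side.**

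| Section | Analysis | Eligibility violators |
|---|---|---|
| Protocol 11.12, SAP 5.5, SAP 11.1 | Primary hypothesis | Excluded |
| Protocol 7.2.2.1, SAP 12.6 | Kaplan-Meier | Included (all patients) |
| Protocol 18.5.1 | Kaplan-Meier | No eligibility limit stated |
| SAP 12.1 | Kaplan-Meier | Excluded |
| SAP 12.4 | Kaplan-Meier | Points to 5.5, written for the primary set |

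The all-patients sentence cannot be fully literal, because time runs from implantation. The Cor family set in SAP 7.3 is its natural meaning. The reference to 5.5 cannot be fully literal either: that chapter also carries the primary endpoint's time window, which cannot govern a 365-day estimate.

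**3. Size for the Kaplan-Meier estimate.** The documents give no violation rate, so v = 1, 3 and 6 violators are assumed. At the planned 2% event rate, the chance that at least one has a 3-month event is 1 − 0.98^v:

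- v = 1: 2.0%
- v = 3: 5.9%
- v = 6: 11.4%

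For the estimate, assume 127 patients, 3 violators and no censoring. With e events among n patients, S = 1 − e/n, and the Greenwood variance is S(1 − S)/n. The log-log 95% limits are S^exp(±1.96·SE), where SE = √[S(1 − S)/n] / (S·|ln S|).

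| Case | e/n | Estimate | 95% CI |
|---|---|---|---|
| All kept | 3/127 | 97.6% | 92.9 to 99.2 |
| Violators removed, one had an event | 2/124 | 98.4% | 93.7 to 99.6 |
| Violators removed, none had an event | 3/124 | 97.6% | 92.7 to 99.2 |
| All kept, the only event is in a violator | 1/127 | 99.2% | 94.5 to 99.9 |
| The same, violators removed | 0/124 | 100% | not calculable |

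The estimate can move either way. Before rounding, the third row is 97.58% against 97.64% in the first. The last row reflects zero events in general: 0/127 would have no log-log interval either.

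No 12-month event rate is assumed in the documents, so no 12-month figure is given. Cumulative risk at day 365 cannot be below that at day 92.

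**4. Does the 20.1 wording matter?** Assume even enrollment, implantation at enrollment and no drop-outs.

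- Planned pace (8.3.7): 127 / 9 = 14.1 per month, and 61 days is about 2.00 months.
- The 114th enrollee reaches day 61 at 114 / 14.1 + 2.00 ≈ 10.1 months, after planned closure at about 9 months. About 14.1 × 2.00 ≈ 28 patients' worth of enrollment time lies in between.
- The stop comes before the 127th enrollment only if 13 / r > 2.00, that is, r below about 6.5 per month. With 5% drop-out the limit is about 3.5 per month. With 10% all 127 are needed and the stop never comes first.
- At 3 per month, about 6 enrolled patients are still short of day 61 when the count reaches 114. It would take 7 or more violators to end below 114.

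**The case against.** The strongest reply is that the all-patients sentence has a narrower meaning. The only patient exclusion listed in protocol 7.2.1 is early termination up to day 61. The next section introduces a method that handles such patients by censoring, so including everyone may simply mean that early terminators stay in. SAP 12.1 does keep them, and the primary and secondary sets then already differ, as 11.9 says. This is plausible and stands as a possible intent. The sentence is nevertheless unqualified, and SAP 12.1 and 12.6 still disagree.

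The second reply is that the 3-month estimate is there to check visit timing, and protocol 8.1.3 asks for consistent assessment across the two endpoints. Holding eligibility constant isolates timing and censoring. This stands for the 3-month estimate and shapes the fix. It does not justify leaving violators out of the 12-month rate.

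The third reply is that little depends on this. SAP 5.3 treats everything outside the primary endpoint as exploratory, and no pass/fail rule uses the Kaplan-Meier result. That is correct.

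On 20.1, the text does name the primary analysis set, so the sentence after it can be read as a gloss on timing. That is also fair.

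**Conclusion.** The contradiction is in the current text and needs one decision. As written, no planned SADE-free rate covers device-exposed violators, and the 12-month rate has no counterpart that does. Severity is minor: the endpoint is exploratory, the example moves the 3-month estimate by less than one percentage point, and its direction is not fixed. These sizes rest on assumed violator counts, the planned 2% event rate and no censoring.

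A reader might infer four stronger things that the documents do not support:

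- **That device events in violators are hidden.** SAP 8.1 places adverse events under the investigational device analysis set, and 8.2.11 takes them from the vigilance report. They are lost from the rates, not from the report.
- **That the primary exclusion is at fault.** It is pre-specified and consistent across protocol 11.12, SAP 5.5 and SAP 11.1.
- **That the Kaplan-Meier rate is necessarily inflated.** Removing event-free violators lowers it slightly.
- **That the 20.1 wording puts the 95% power at risk.** One patient fewer than 114 does take power from 97.3% to 92.3%, but the optional stop would not bind at the planned pace, and patients already enrolled would usually make up the number.

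**What to change.** 1. **SAP 12.1:** delete the eligibility exclusion, so that the 3- and 12-month Kaplan-Meier estimates use every consented patient with a Cor Family implantation attempt, with early terminators censored.
2. **SAP 12.4:** state that the patient exclusions in chapter 5.5 do not apply to this endpoint. The consent requirement is kept through the set definition in item 1.
3. **SAP chapter 12:** also report the 3-month estimate without violators, so that the timing check against the primary rate stays like for like.
4. **Minor wording, protocol 20.1:** align the membership sentence with 11.12 and with the day-61 rule in 7.2.1.

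The pre-specified primary exclusion stays as it is. The cost is one clause deleted, two short wording changes and one extra output, with no new data collection. The Kaplan-Meier estimate may shift slightly in either direction. If the early stop is ever used, enrollment may run a few patients longer.
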